Re-ulceration, re-infection, re-amputation and hospital re-admission after partial foot amputation for digital gangrene is well documented in the literature in both diabetic and PAD cohorts(6). Across the literature, rates of re-amputation at five years post-index surgery for diabetic foot complications range from 45-65% (6, 7). A recent study by Collins et al reported that, out of 146 Irish patients undergoing minor amputations, 43% (n=63) required further ipsilateral amputation, 21 (14.4%) of which were trans-tibial or trans-femoral(8). Chronic kidney disease, diabetes with or without poor glycaemic control, peripheral neuropathy, peripheral arterial disease, ongoing tobacco smoking, obesity (BMI >30), concurrent sepsis at the time of index operation have all been identified as independent risk factors for amputation failure and the need for revision(9-11). While numerous studies have investigated patient-dependent factors predictive of amputation failure, there is a dearth of evidence examining the impact of surgical technique on this commonly performed procedure.

An exhaustive search of the literature surrounding surgical technique and outcomes after ray amputation yielded several papers on the benefits of various soft tissue flaps for covering wound defects but just one detailing a particular methods of bone transection. However, Moodley et al focused on the use of a Gigli saw, which is beyond the scope of this feasibility

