2.2 Secondary Objectives

1. To determine the effect of oscillating microsaw compared to bone cutters for toe amputation on rates of surgical reintervention at six months;
2. To determine the effect of oscillating microsaw compared to bone cutters for toe amputation on re-infection rates;
3. To determine the effect of oscillating microsaw compared to bone cutters for toe amputation on time to surgical wound healing;

4. To determine the effect of oscillating microsaw compared to bone cutters for toe amputation on wound-related hospital readmissions at six months;
5. To determine the effect of oscillating microsaw compared to bone cutters for toe amputation on ulcer healing;
6. To determine the effect of oscillating microsaw compared to bone cutters for toe amputation on ulcer recurrence;
7. To determine the effect of oscillating microsaw compared to bone cutters for toe amputation on osteomyelitis recurrence in the affected foot;
8. To determine the effect of oscillating microsaw compared to bone cutters for toe amputation on resection specimen margin culture positivity;
9. To determine the effect of oscillating microsaw compared to bone cutters for toe amputation on patient-reported post-operative pain, as measured by the Verbal Rating Scale (VRS)(13, 14);
10. To determine the effect of oscillating microsaw compared to bone cutters for toe amputation on patient-reported health-related quality of life (HR-QoL) at 6 weeks and 6 months post-operatively, as measured by the EQ-5D-5L tool(15)

3. Study Design and Endpoints:

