4.2 Exclusion Criteria

1. Patients with significant peripheral arterial disease, as defined by ABPI <0.4 or digital pressures of <50mmHg, not undergoing concurrent revascularisation;
2. Patients unfit for surgery;
3. Patients unable to provide informed consent.

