6.1 Follow up

All patients will be followed up with an x-ray at 6 months post-operatively to assess for bony healing, as is common practice in orthopaedic surgery. Any recurrence of symptoms, post-operative complications or concerns will be recorded. As per usual vascular practice, patients will be followed up in the community post-discharge and receive regular wound care from public health nurses. In order to determine approximate time from surgery to wound healing, sequential wound pictures will be sent on a fortnightly basis by the PHN to a secure HSE email account used by the trial investigators.

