6.3 Loss to follow-up

Any loss to follow up will be documented and explained to the best ability of the investigator. During consent, the importance of follow-up will be impressed upon, and any non-attendance to clinic or imaging will be followed up by a member of the team and the patient will be encouraged to attend if possible. Any reasons not able to attend will be recorded.

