7.4 Event Reporting

All adverse events will be reported directly to the either the site or principal investigator. Recurrent adverse events or serious adverse events in isolation will be reported in turn to the local Ethical Committee and the risk assessment department for risk analysis.

8. Statistical considerations:

Post intervention, all patient outcomes will be recorded and assessed on intention to treat basis. We expect a certain degree of crossover from the bone cutter trial arm to bone saw trial arm, as is reflected in daily surgical practice. Furthermore, we expect a small number of patients may ultimately not undergo treatment as initially planned. Any losses to follow up will be reported. There are no studies investigating this particular trial question, as such there is no data on which to base a power calculation. For this pilot trial, we aim to recruit 20 patients into each arm i.e. 40 patients in total. All analyses will be performed on an intention to treat basis. The statistical analysis will be blinded. Binary outcomes will be analysed using the Chi-Square test. Non-parametric continuous variables will be compared using Mann-Whitney U Test. The time between surgery and measurable endpoints will be compared using Kaplan-Meier Survival Curves.

9. Ethical Considerations:

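### The Kaplan-Meier plan for wound healing has no rule for death or major amputation before healing; if these patients are censored, the curve overstates the proportion healed

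*Combined protocol and SAP*

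**What the plan says.** Section 2.2, objective 3, asks for the effect of the oscillating microsaw against bone cutters "on time to surgical wound healing". Section 6.1 says how healing time is to be observed: "sequential wound pictures will be sent on a fortnightly basis" by the public health nurse. It gives no point at which the pictures end.

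The only analysis text for times is one sentence in section 8: "The time between surgery and measurable endpoints will be compared using Kaplan-Meier Survival Curves". It does not mention healing by name, but healing is the secondary objective expressed as a time from surgery, so the sentence covers it.

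Four other places come near the question without answering it:

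- Section 8 states that "all patient outcomes will be recorded and assessed on intention to treat basis". This fixes the arm in which a patient is counted. It does not say whether a death or a major amputation is an event, a censoring or something else.
- Section 8 adds "Any losses to follow up will be reported", and section 6.3 that "Any loss to follow up will be documented and explained to the best ability of the investigator". Both concern documentation of losses.
- Section 7.1 lists major ipsilateral amputation as an adverse event to be recorded and reported.
- Section 7.3 mentions death only within the definition of a serious adverse event.

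**The concern.** A patient who dies or loses the foot can no longer heal the index wound. Kaplan-Meier treats a censored patient as someone who could still heal at the same rate as those who remain under observation. If these patients are censored, the method in effect credits them with healing that cannot happen, and one minus the Kaplan-Meier curve rises above the proportion of randomised patients whose wound heals.

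The event is foreseeable. The background cites an Irish cohort of 146 patients with minor amputation, of whom "43% (n=63) required further ipsilateral amputation, 21 (14.4%) of which were trans-tibial or trans-femoral". What is at stake is the absolute healing curve plotted for each arm, and any proportion healed that a reader takes from it.

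**Working it through.** **Inputs from the documents.** 20 patients per arm (section 8). For major amputation, 21/146 = 14.4%; for any further ipsilateral amputation, 63/146 = 43.2%, so the cited percentages reproduce. The plan gives no expected healing proportion, death rate or time horizon for healing, so it has no figure of its own on this point to reproduce.

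**Assumed inputs.** True proportion healed H = 50% or 60%. Proportion with death or major amputation before healing C = 14.4% (the cohort figure) or 7.2% (half of it). Constant cause-specific hazards, and censoring at the competing event.

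**Formula.** Let T = H + C. The total cumulative hazard is L = -ln(1 - T), and healing's share of it is L × H/T. With competing events censored, the curve reads 1 - exp(-L × H/T). The overstatement is that value minus H.

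| C | H | T | L | L × H/T | 1 - KM | Overstatement |
|---|---|---|---|---|---|---|
| 14.4% | 50% | 0.644 | 1.033 | 0.802 | 55.2% | 5.2 points |
| 14.4% | 60% | 0.744 | 1.363 | 1.099 | 66.7% | 6.7 points |
| 7.2% | 50% | 0.572 | 0.849 | 0.742 | 52.4% | 2.4 points |
| 7.2% | 60% | 0.672 | 1.115 | 0.995 | 63.0% | 3.0 points |

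The cumulative incidence returns H itself in each row.

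**Timing.** The constant-hazard values lie between two extremes. If every competing event follows the last healing, the overstatement is zero. If every one precedes the first healing, it is H/(1 - C) - H. At C = 14.4% that is 0.50/0.856 - 0.50 = 8.4 points, or 0.60/0.856 - 0.60 = 10.1 points.

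**One arm of 20.** At 14.4%, 20 × 0.144 = 2.9 patients are expected to have a competing event. Take 12 healed (60%) and 3 competing events. One minus Kaplan-Meier is 12/17 = 70.6% if the three come first, 66.8% in one interspersed order, and 60.0% if they come after the last healing. A simulation of arms of 20 (H = 60%, C = 14.4%, no other loss, 8,000 runs) gave a mean of 66.7% for one minus Kaplan-Meier against 60.0% for the cumulative incidence.

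**Comparison with sampling error.** At H = 60% the one-arm standard error is sqrt(0.6 × 0.4/20) = 0.110, or 11.0 points. At 50% it is sqrt(0.5 × 0.5/20) = 0.112, or 11.2 points.

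**The case against.** The strongest reply is that the plan nowhere promises a proportion healed. It promises a comparison of times between arms, and a comparison of healing hazards among patients still at risk is not biased in this way. That stands, and it limits the point to the absolute curve. The curve will nevertheless be drawn, and readers will take percentages from it.

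A reader might also infer more than the documents support:

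- *That the plan censors these patients.* It does not say so. Pictures plainly end at death, but section 6.1 does not say that they end at major amputation. Censoring is inferred from usual practice; the point is that nothing in the plan prevents it.
- *That the arm comparison will be wrong.* The gap between the plotted curves would be distorted if competing-event rates differed by arm. With 60% truly healed in both arms and rates of 5% and 20%, the curves would read 62.1% and 70.1%. Nothing in the documents suggests that the rates differ.
- *That the primary endpoint or the future sample size is compromised.* The primary efficacy endpoint (section 3.2.1) is a count of patients with reintervention and does not use this curve. No section says that healing will feed the future power calculation.
- *That 14.4% is the rate to expect here.* It comes from another cohort, has no stated time horizon and may include amputations after healing. The trial also excludes patients with severe arterial disease, "as defined by ABPI <0.4 or digital pressures of <50mmHg, not undergoing concurrent revascularisation". Deaths, on the other hand, are not counted in it. It serves only to set a scale.

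A last objection is that minor re-amputation before healing also lacks a rule and was commoner in that cohort: 63 - 21 = 42 of 146, or 28.8%. That is fair. It is a separate question, which the change below does not settle.

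**Conclusion.** The omission is real, and the direction of the error is certain if these patients are censored and others heal later. The size is not known. An error of 2 to 7 points is plausible, but it rests on assumed healing of 50-60%, constant hazards and an outside event rate or half of it. It is smaller than the sampling error of one arm, though unlike sampling error it would not shrink with more patients. It touches one of ten secondary objectives in a 40-patient feasibility study. The severity is minor, and the change is worth making because it costs almost nothing.

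**What to change.** In section 8, for time to surgical wound healing, replace one minus Kaplan-Meier with the cumulative incidence of healing by arm (Aalen-Johansen estimator), treating death and major ipsilateral amputation before healing as competing events. Record the dates of both events for every patient.

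Keeping these patients in the Kaplan-Meier risk set as unhealed to the end of follow-up gives exactly the same answer only when there is no other censoring. Since the plan allows for losses to follow-up, the cumulative incidence is the safer choice, although the difference is small: 0.2 to 0.5 points in simulation at 60% healing with 10-20% loss.

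The cost is one or two sentences of SAP text, standard software and two explicit date fields. The downside is that reported healing looks slightly less favourable and there is a little more analysis work. The dates should be collected from the start, because they are hard to recover later.

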9.1 Ethical approval

Ethical approval will be processed by the Research Ethics Committee at the University Hospital Galway Medical Ethics Committee.

9.2 Data Protection

All data shall be managed in the strictest confidence by approved trial investigators in accordance with Irish data-protection law. Datasets will be anonymous, encrypted and stored in a secure centralised sever (REDCap).

10. Discussion:

At present, ray amputation can be performed using a bone cutters or a bone saw to transect the metatarsal shaft, depending on institutional availability and surgeon preference. There is a dearth of published literature comparing outcomes achieved between the two techniques.

Certainly, there has been no randomised controlled trials published. This randomised controlled feasibility study aims to provisionally compare the value and safety profile of two different surgical techniques. An initial feasibility study was selected as a significant number of patients are needed to power a full study. We plan to recruit from multiple sites after the initial cohort has been selected.

References:

2. Emerging Risk Factors C, Sarwar N, Gao P, Seshasai SR, Gobin R, Kaptoge S, et al. Diabetes mellitus, fasting blood glucose concentration, and risk of vascular disease: a collaborative meta-analysis of 102 prospective studies. *Lancet*. 2010;375(9733):2215-22.
